## APPROACH

We propose to conduct a randomized controlled trial to examine the feasibility, efficacy, and comparative effectiveness of two community-based health promotion programs for older adults with OA: our evidence-based *Fit and Strong!* PA program and an enhanced program, *Fit and Strong! Plus*, that includes elements common to two existing evidence-based behavior change dietary interventions.

Conceptual Model—We have used Social Cognitive Theory (SCT) (Bandura , 1982; Bandura 1989) and Self Determination Theory (SDT) (Deci and Ryan 1991; Deci and Ryan 1980; Deci and Ryan, 1985) to guide model development, intervention design, and selection of study measures. SCT specifies that behavior change occurs as a result of the dynamic interaction between modifications in behavior, cognition (self-efficacy, perception of barriers), and the environment (social support), and that modeling and reinforcement can be used to encourage change. SDT is a broad-based theory of human motivation (Ryan and Deci , 2000) that is increasingly cited to explain how personal or intrinsic motivation can lead to increased physical activity and improved eating patterns (Deci and Ryan, 1985). According to SDT, an individual's increased intrinsic motivation to improve eating and activity patterns should positively relate to self-efficacy and the ability to overcome barriers and solicit support.

**Figure 1.** Conceptual Model for Proposed Fit and Strong! vs. Fit and Strong! Plus Comparison Study

Our Conceptual Model (Figure 1) shows that demographic, disease, and arthritis functional class variables are antecedents that will be controlled in multivariate analyses. These antecedent variables predispose some participants to be more responsive to both the PA and PA/diet interventions. SE/motivation for exercise and SE/motivation for dietary behaviors are expected to change as a result of exposure to treatment. They are also expected to mediate the impact of the interventions. ***Both the dietary change and PA interventions tested will use social modeling, exercise logs or food diaries, individualized goal setting, and shared group problem solving to increase mastery and goal achievement in small incremental steps to enhance self regulatory skills. We hypothesize that customary Fit and Strong! will increase SE and intrinsic motivation for exercise only; whereas Fit and Strong! Plus will increase SE and motivation for both exercise and weight loss. These mediators will impact the interim primary outcome of physical activity and dietary behaviors. These improved behaviors, in turn, are hypothesized to impact the more distal primary outcomes of exercise maintenance and weight loss along with the associated secondary outcomes shown.***

will be repeated 4 times at 3 sites to achieve a final targeted baseline sample of 400 participants (i.e., 2 interventions x 3 sites x 4 replications x 17 participants = 408 participants). Outcome measures will be obtained at baseline, 2, 6, 12 and 18 months (see Figure 2, Projected Consort Flow Diagram, Appendix C).

**Settings**—We will partner with the Chicago Park District and Westside Health Authority (WHA) to conduct the trial. Although we require 3 sites to conduct the trial, the Park District has identified 4 sites that can participate, and WHA has identified 1 site. The Park sites include Smith Park (Northwest), Wicker Park (Northwest), Washington Park (Southeast), and Columbus Park (Southwest), and the WHA site includes their location on the westside (see more information about the sites in Appendix D). **All sites are staffed by nationally certified exercise instructors who will be trained separately to conduct either customary Fit and Strong! or Fit and Strong! Plus. (See letters from [name], CEO, Chicago Park District from [name], CEO, National Recreation and Park Association, and from [name], CEO, Westside Health Authority in Section 14).**

**Recruitment**—Recruitment will begin in Year 1 and continue through Year 2. Based on our experience enrolling 486 persons in our effectiveness trial, we will use multiple, diverse recruitment methods to screen an estimated 888 older adults in order to identify 533 (60%) who will meet all study inclusion criteria, 400 of whom will elect to participate in baseline measurement and the two interventions. The *Arthritis Foundation/Heartland Region* will assist with recruitment (see Section 14). Their database includes 7,000 older adults with OA. Chapter staff will do direct mailings to older adults with OA *residing in zip codes served by study sites*. Staff will also publicize the study and refer older adults who call their information hotline. *Park District* sites will publicize the study in quarterly activity catalogs mailed to persons over 60 living in the same zip codes. The *UIC Department of Geriatrics* has a mailing list of 1,500 patients to whom it will send mailings based on zip codes. They also partner with the *Jesse Brown Veteran's Administration Hospital*, which provides access to an additional 4,000 people 65+ (see Section 14). Research staff will speak to groups about the study at all sites and obtain contact information from interested persons. Potential participants will be called to conduct follow up eligibility screens. Recruitment advertisements will ask interested persons to call a central registry number that will be fielded by research staff who will record contact information, screen callers for eligibility and schedule interviews for those deemed eligible. **These procedures have been approved by the UIC IRB and were used successfully for the current Fit and Strong! Plus pilot.**

**Procedures and Data Collection**—We have experience training research staff for health risk reduction interventions and will use the same procedures we have used in the past. Training will take place prior to the initial interview and will cover an overview of the study, informed consent, interviewing skills, data check/editing, anthropometrics, participant contact (phone call etiquette and schedule for mailings), protocol for compensating participants, data scanning, and data packet construction. **Prior to the pilot we developed an interviewer training manual covering all data collection procedures (see Training Manual, Appendix E).** Project staff will obtain informed consent at the baseline interview. Participants will be paid \$25 per interview for each of 5 interviews. In addition, four participants at each participating site (2 from each study group) who complete each posttest will be randomly selected to receive a \$50 gift certificate to a local store of their choice. Participants will also be paid \$50 for participating in 24-month interviews. CRHA staff will make at least 10 attempts to schedule interviews on different days of the week and at different times of the day before giving a case a final disposition. Posttest measurement *will take place at intervention sites* and will be scheduled on separate days for the two intervention groups.

Additionally, if participants complete data collection for the ancillary study (Protocol # 2013-0098) prior to their baseline/post-test interview, the height and weight data collected by the ancillary study will be used as part of the #2012-0277 study. Protocol # 2013-0098 has received approval through March 19, 2014. The study is called, "Effect of Community-based Lifestyle Interventions on Serum Biomarkers of Cancer Risk in Overweight and Obese Older Minority Adults with Osteoarthritis: A Randomized Trial". The data collection site for this protocol is the Integrative Physiology Lab in the UIC Disability, Health & Social Policy Building, at [name].

**Randomization**—After obtaining informed consent, participants will be assigned to Fit and Strong! or Fit and Strong! Plus using a randomized block design with blocks consisting of approximately 17 participants at each of the 3 sites. Within each block we will stratify by American College of Rheumatology (ACR) functional classes (I, II, or III) to achieve balance on arthritis severity by group. The random permutation of block sizes will help to minimize manipulation of an assignment.

**Inclusion/Exclusion Criteria**—*Inclusion criteria* include LE OA (hips, knees, ankles, feet, lower back), age 60+, no current participation in a regular exercise program, a calculated BMI of  $>=25 - 50 \text{ kg/m}^2$  (upper limit used in ORBIT) ([name] et al., 2010) and willingness to participate in measurement and intervention procedures. The study rheumatologist will examine participants at the baseline interview to confirm presence of LE OA and determine ACR functional class. *Exclusion criteria* include severe cardiovascular disease, active thrombophlebitis, recent pulmonary embolus, an acute systemic illness, poorly controlled diabetes, other health conditions that might preclude exercise training, age  $<60$ , current participation in organized PA, uncomplicated hip or knee surgery within the previous 6 months or complicated surgery within the past year, steroid injections in either knee or hip within the previous three months, or diagnosis of rheumatoid arthritis. Participants with blood pressure readings 180/110 mm Hg or higher or 90/50 mm Hg or lower will be excluded.

**Intervention Instructors**—*Exercise instructors delivering the programs will be certified by at least 1 of 10 possible nationally recognized certification bodies* (e.g., ACSM, ACE, etc.). Certified exercise instructors (CEIs) will be trained separately to conduct either Fit and Strong! or Fit and Strong! Plus. The CEIs will lead exercise sessions, maintain participant attendance records, and negotiate participant adherence plans during week 6. They will also facilitate the group problem solving sessions (see Fit and Strong! Plus Instructor Manual in Appendix F). If both programs are offered at the same site on the same day, we will schedule one program in the morning and the other in the afternoon to minimize contact between both participants and instructors. An alternative will be to schedule one program Mon, Weds, Fri and the other Tues, Thurs, Sat. Instructors for customary Fit and Strong! will participate in *an 8-hour training protocol* that we developed and refined over multiple studies. The protocol reviews theories used to design Fit and Strong!, findings from completed research, along with detailed information and hands-on modeling of the exercise components (warm ups, flexibility, aerobic conditioning, strength training, cool down), role playing group problem solving processes, and negotiating PA contracts. Fit and Strong! Plus instructors will participate in *a 12-hour training protocol* for Fit and Strong! Plus that includes the full Fit and Strong! instructor training plus training on *diet and weight management*. The training will cover the *contribution of excess weight to disability and exacerbation of OA symptoms, the significance of a minimum 5% weight loss* for this population, components of a healthy diet, the new USDA my plate (choosemyplate.gov), food shopping on a budget, healthy meal preparation, handling situations that trigger impulse eating, tips for healthy eating at restaurants, ethnic eating, cultural aspects of eating preferences, and choosing foods at special occasions. **Drs. [name] and [name], both of whom participated in the pilot training, developed the draft protocol.** The protocol includes role play for facilitating diet-focused group discussion/problem solving sessions and negotiating *PA and diet adherence contracts* (see Instructor Training, Appendix G).

**Attendance/Retention**—Participants will be notified of the dates of the classes, and those who anticipate missing more than three classes will be asked to defer to a subsequent iteration. Participants in the Fit and Strong! effectiveness trial attended 79.2% of possible sessions. ***The ORBIT trial had 95% retention post-intervention and 92% at 18 months ([name] et al., 2010). Attendance during the current pilot has been 85%.*** To maximize retention during the facility-based portion of the study, we take attendance and call participants who miss any sessions. We will call anyone who withdraws from the program to obtain reasons for dropout. ***Of 11 persons who enrolled in the current Pilot, 10 are actively engaged at 4 weeks.***

**Exercise Components**—*Both interventions encompass identical exercise routines. All exercises are accompanied by music, and the instructors progressively challenge participants' balance.*

**Flexibility.** Sessions begin and end with 10-minute warm ups and cool downs involving neck, trunk, and extremity range of motion exercises. Static and dynamic sitting and standing balance exercises are used and floor exercises are conducted during cool down in the latter weeks of the program.

**Aerobics.** Fitness walking progresses from maximum capacity at baseline to 20 minutes of sustained walking. Intensity is 40% - 60% of maximum heart rate (13 - 15 on the Borg Scale of Perceived Exertion) (Borg, 1982). Participants are taught basic low impact aerobic routines to maximize SE for enrollment in that type of program after Fit and Strong! ends if that is their choice for a maintenance PA program.

**Strengthening.** LE strengthening exercises use a graded, task-specific approach (sit to stand and postural stabilization). We implement resistance exercises using cuff weights and exercise bands (Fisher et al., 1991; Fiatarone et al., 1994). Resistance is progressively increased by adding weight in increments of 0.5 lbs. Since ability to rise unassisted from a chair or the floor is critical for independent functioning, strengthening exercises incorporate progressive sit-to-stand and floor-to-stand activities targeting these functions.

**Physical Activity Logs.** Participants log their PA (e.g., number of repetitions, sets, weight, and exertion level) in the Participant Manual at the end of each exercise session to reinforce their sense of mastery over time.

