**Table 3: Proposed Study Measures**

**A. Screening Measures**

10-item Short Portable Mental Status Questionnaire (Kahn et al., 1960)	
 
• Screens for moderate-to-severe cognitive impairment
 
• Good reliability and validity (Kane and Kane, 1981)
 
• Ineligible if answer more than three items incorrectly
 

Physical examination of joints and muscles by study rheumatologist	
 
• Determines clinical presence of OA in LE joints
 
• Rates functional significance using ACR arthritis functional class (Hochberg et al., American College of Rheumatology, 1992)
 

History of falls	
 
• Self-reported number of falls in last 2 years (Mobility and aging survey developed and used by the Centers for Disease Control and Prevention Healthy Aging Network).
 

B. Dependent Measures: Assessed at baseline, 2, 6, 12 and 18 months	
Primary Proximal Outcomes	
National Cancer Institute (NCI) Percent Energy from Fat Screener (Thompson et al., 1998)	
 
• Assesses usual daily intake from fat over previous 12 months
 
• Correlates strongly with true dietary intake (Thompson et al., 2007)
 

NCI Fruit and Vegetable Screener (Thompson et al., 2000)	
 
• Obtains fruit and vegetable intake during a typical day
 
• Correlates strongly with true dietary intake (Thompson, 2002)
 

Block Brief Food Frequency Questionnaire (FFQ) (Block et al., 1990)	
 
• Assesses 6-month changes in energy intake, % energy from fat, saturated fat, grams of fiber, servings of fruit and vegetables based on 70 food items
 
• Reliability and validity demonstrated in a wide range of age, gender, income and ethnic groups including low-income women (Coates et al., 1991; Block et al., 1992; Lanza et al., 2001; French et al., 2000)
 

Primary Distal Outcomes	
Weight and BMI	
 
• Weight measured without shoes using same calibrated Tanita BWB-800 digital scale
 
• Height measured without shoes to calculate BMI using Seca 214 portable stadiometer
 

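### Ancillary-study weights can enter the primary weight outcome with no time window, no equipment match and no same-source rule

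*Combined protocol and SAP*

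**What the plan says.** Procedures and Data Collection sets a condition, "if participants complete data collection for the ancillary study (Protocol # 2013-0098) prior to their baseline/post-test interview", and a consequence, "the height and weight data collected by the ancillary study will be used as part of the #2012-0277 study". The trigger is the order of the two visits, not the absence of a trial weight. The section then locates the ancillary measurements: "The data collection site for this protocol is the Integrative Physiology Lab in the UIC Disability, Health & Social Policy Building". Trial post-test measurement, by contrast, "will take place at intervention sites".

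Table 3 places weight and BMI under "Primary Distal Outcomes". It specifies "Weight measured without shoes using same calibrated Tanita BWB-800 digital scale" and "Height measured without shoes to calculate BMI using Seca 214 portable stadiometer". The assessment schedule reads "Outcome measures will be obtained at baseline, 2, 6, 12 and 18 months".

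The following are not stated:

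- which scale the laboratory uses, whether it has been checked against the trial scale, and whether shoes are removed there;
- how long before the interview an ancillary weight may have been taken;
- whether a trial weight is also taken, and which value takes precedence;
- whether a person's weights must come from one source across visits;
- whether the source and date of each weight are recorded.

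The Data Analysis section has no term for the source of a weight and does not say that the actual weighing date is used. The sensitivity work under Missing Data concerns dropout patterns only.

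**The concern.** Weight is the outcome on which the Power Analysis rests, and the model in Data Analysis estimates its change within person over time. Two things can then go wrong.

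First, if a person is weighed in the laboratory at some visits and on the trial scale at others, any difference in scale, clothing or procedure appears in that person's change as if it were real. The rule works visit by visit, and nothing shows that the ancillary schedule matches the five trial visits, so such switching is possible.

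Second, a weight taken some weeks before a post-test misses whatever loss occurs in between. If the Plus arm is losing faster at that time, the missed loss is larger in Plus and the arm difference shrinks, even when both arms are weighed equally early.

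The ancillary study's title restricts it to overweight and obese older minority adults, so the source of a weight may also be associated with race or ethnicity.

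**Working it through.** The plan gives no figure for this point, so there is none to reproduce. The calculations below only show how large the effect could be.

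**Inputs from the plan**
- Weight goal in the Fit and Strong! Plus description: at least 5% loss at 6 months, then maintained.
- Power Analysis: an effect size of 0.2 equated with a 5% weight difference at the end of the study, linear change over time, cross-time correlation 0.9, about 300 subjects.
- Last listed visit: 18 months.

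**Assumptions (not in the plan)**
- An ancillary weight taken 2-4 weeks before the post-test.
- 25-50% of participants with an ancillary weight at that visit.
- A comparator arm with no weight change.
- Scale offsets of 0.5-2% of body weight.
- Two-sided alpha of 0.05.

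**1. Early weighing**

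Attenuation of the arm difference = (difference in weekly loss between arms) × (weeks early) × (share affected).

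*Month 6, with 5% lost over 26 weeks.* The weekly loss is 5/26 = 0.19 points.
- Per person: 2 × 5/26 = 0.38 to 4 × 5/26 = 0.77 points missed.
- Arm difference: 0.38 × 0.25 = 0.10 to 0.77 × 0.50 = 0.38 points, or 2-8% of the 5% target.

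*Linear path to 18 months (78 weeks), as in the Power Analysis.* The weekly loss is 5/78 = 0.064 points.
- Per person: 0.13 to 0.26 points missed.
- Arm difference: 0.13 × 0.25 = 0.03 to 0.26 × 0.50 = 0.13 points, or about 0.6-2.6% of the target.

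*Loss reached by month 6 and then maintained.* The slope at 12 and 18 months is zero, so the attenuation there is about zero.

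*Month 2, on the 26-week path.* Loss at 8 weeks is 8 × 5/26 = 1.5 points. Weighing 2-4 weeks early misses 0.38/1.54 = 25% to 0.77/1.54 = 50% of an affected person's change. The absolute error is the same as at month 6, but it is large relative to the change at that visit.

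**2. Scale offset**

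- Implied SD = 5%/0.2 = 25% of mean weight, so offsets of 0.5%, 1% and 2% are 0.02, 0.04 and 0.08 SD.
- Change-score variance without an offset = 2(1 − 0.9) = 0.20 SD².
- If a share f of each arm switches source between baseline and endpoint, the variance becomes 0.20 + offset² × f(1 − f). In the worst case tried (2% offset, f = 0.5), this is 0.20 + 0.0064 × 0.25 = 0.2016.
- Power with 150 per arm, without attrition: 0.972 with no offset and 0.971 in that worst case. This simplified change-score calculation is used only to compare the two cases. It does not reproduce the plan's power of 0.9.
- Bias arises only if the switching share differs between arms. With a 10-point difference it is 0.10 × 0.5% = 0.05 to 0.10 × 2% = 0.20 points, or 1-4% of the target.

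**The case against.** A reader might infer that the plan contradicts itself on the scale. The documents do not show this. The laboratory's equipment is not described. The trial itself runs at three sites, so the same scale in Table 3 may mean the same model, and the laboratory could own one. Data-collection procedures are also referred to a training manual in an appendix that is not part of the public text. What stands is that compliance is not assured. The difference in place, laboratory against intervention sites, is explicit.

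A reader might also infer that ancillary weights replace trial weights. That is the natural reading, but the text says only that they will be used and does not say that the trial weight is omitted. Attendance at the trial visit is not certain either. The attrition paragraph under Process Measures allows post-tests by telephone, and for such a person the ancillary weight may be the only measured one. This is a good reason to keep ancillary weights as a fallback.

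The strongest objection concerns size. Randomized arms with similar ancillary participation would share any scale offset, so it largely cancels in the comparison. The month-6 attenuation uses the steepest plausible slope. On the linear path behind the sample size it falls to about one third, and with maintained weight it vanishes at the later visits. The share, the interval and the flat comparator are all assumed, and any loss in the comparator reduces the attenuation further. All of this stands. It does not reach the timing effect during active loss, which needs no imbalance between arms in participation or in weighing dates.

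Finally, a fallback rule still allows a person's source to change between visits. That is true. It would be rarer, and the scale check, the source record and the sensitivity analysis would make it visible.

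**Conclusion.** The concern holds in a limited form. An open-ended rule admits weights from another place and an earlier date into the powered outcome, and neither Table 3 nor the analysis plan deals with the consequences. Mixed sources and dates within a person are possible; the documents do not show how often they occur, or that they occur at all.

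Under the stated assumptions the arm difference would be attenuated by about 0.1-0.4 points at month 6, about 0.03-0.13 points on a linear 18-month path, and close to zero once weight is stable. A balanced scale offset is mainly noise and leaves power at about 0.97 in the simplified calculation. For an individual, an error of 0.4-0.8 points during active loss can matter when that person is classified against the 5% goal.

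A stronger reading, that the primary comparison is seriously biased, is not supported. The change is worth making because it gives a clearly better rule for a primary outcome at very little cost.

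**What to change.** - At every in-person trial visit, weigh the participant on the trial scale and use that weight in the analysis.
- Use an ancillary weight only when no trial weight is available and the ancillary weight falls within a prespecified window around the trial visit, for example 7 days.
- Name the laboratory scale and check it against the trial scale.
- Record the source and date of each weight.
- Repeat the primary weight analysis without ancillary values.

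The cost is about a minute per visit, one or two data fields and one sensitivity analysis. For weights already collected, the source and date flags and the sensitivity analysis can still be added if the ancillary records hold the measurement dates.

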**Data Analysis**—The basic trial design consists of one between-participant effect (customary Fit and Strong! vs. Fit and Strong! Plus) and one within participant effect (time) variable. Although the structure of the study is factorial, data analysis will be based on the general linear mixed model in a regression format (this approach is

more flexible than traditional ANOVA). Because the same persons will be measured repeatedly, the conventional regression assumption regarding independence of error terms is untenable. There are two ways to deal with this problem: generalized estimating equations (GEE) and random effect models. GEE is simpler but requires more power and a stronger set of assumptions regarding missing data. Random effect models can be used to analyze longitudinal data and permit a more sophisticated approach to analyses than GEE at the cost of some additional complexity. The basic model for data analysis is

$$Y_{it} = \beta_0 + \beta_1 Plus_i + \beta_2 Time_{it} + \beta_3 Plus_i * Time_{it} + \beta_4 ARA_i + u_i + e_{it}$$

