where  $Y_{it}$  represents a particular outcome variable for person  $i$  at time  $t$ , *Plus* is a dummy variable for the Fit and Strong! Plus effect, relative to customary Fit and Strong!, *Plus\*Time* represents the interaction with time, *ARA* is a covariate,  $u_i$  is the random effect for person  $i$  and  $e_{it}$  is a person-time specific error term. The *Plus\*Time* interaction tells us whether the rate of change with respect to time is greater (or less) in the Plus condition compared to customary Fit and Strong!. As shown, the model is for a continuous outcome, but it can be estimated for a wide variety of outcome variables (e.g., logistic regression and ordered logistic regression models). Time can be represented in multiple ways in addition to the simple linear effect shown here. By including the square of time we can test whether the effects of time are non-linear, and by including properly coded dummy variables for discrete time, we can test more specific hypotheses regarding non-linear effects. A crucial assumption of such models is that the person-specific error term,  $u_i$ , is uncorrelated with the remaining variables, which is plausible given the randomized design. The model, as written, assumes an “exchangeable” correlation matrix among the errors. However that assumption can be relaxed by using simple auto-regressive or Toeplitz (banded) correlation structures. All analyses will be done using Stata.

Analyses of secondary outcomes will examine the magnitude of between and within group differences at all time points to determine whether the addition of a diet component to Fit and Strong! benefits these outcomes (as expected) or is neutral or harmful with respect to certain outcomes. Exploratory analyses will evaluate movement on the new readiness for total joint replacement measure, and will examine patterns and trends in healthcare utilization, healthcare cost, and quality of life between and within the two study groups.

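### Site and replication shape the assignment but are absent from the analysis model; taken alone this slightly overstates the standard error of the Plus-by-Time term, though the net direction of error is unknown

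*Combined protocol and SAP*

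**What the plan says.** The Randomization paragraph under APPROACH assigns individuals "using a randomized block design with blocks consisting of approximately 17 participants at each of the 3 sites". It then adds a stratifier: "Within each block we will stratify by American College of Rheumatology (ACR) functional classes (I, II, or III".

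The design paragraph just before Settings says that the two-arm set "will be repeated 4 times at 3 sites to achieve a final targeted baseline sample of 400 participants", and counts the sample as "2 interventions x 3 sites x 4 replications x 17 participants = 408 participants". That makes 3 x 4 = 12 site-waves, each holding both arms, and 24 arm-specific classes. The Randomization paragraph does not name replication. Blocking by replication is an inference from this count.

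The basic model in the Data Analysis paragraph is "Y_{it} = \beta_0 + \beta_1 Plus_i + \beta_2 Time_{it} + \beta_3 Plus_i * Time_{it} + \beta_4 ARA_i + u_i + e_{it". ARA is described only as a covariate; I take it to be arthritis functional class. The arm comparison is the Plus-by-Time term: this "interaction tells us whether the rate of change with respect to time is greater (or less) in the Plus condition". The section then allows other codings of time and other error correlations, but adds no term for site, replication or class. The Conceptual Model section promises control for patient characteristics, disease factors and functional class. Site and replication are not among them.

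Under Intervention Instructors, each instructor is trained for one program or the other, and the two programs are scheduled apart.

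**The concern.** An analysis should normally carry the factors used to form the comparison. Both arms sit in every site-wave, so a neighbourhood or seasonal trend that both share drops out of the arm difference. The written model still counts that trend as residual noise. The reported standard error is then larger than the design requires, and some power is given away.

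A site or wave main effect alone would do little, because the person intercept already absorbs differences in level. Differences in change are what matter, so the missing terms are the interactions with time. If the plan stays silent, site or wave adjustment also becomes a choice made after the data are seen.

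**Working it through.** **The plan's own figure.** The documents give no site-wave variance, so there is nothing to reproduce on this exact point. The nearest figure is the Power Analysis: about 300 subjects for power .9, effect .2, cross-time correlation .9 and 5% attrition per time point. Alpha is not stated; I assume .05 two-sided. For a linear trend over five equally spaced visits with exchangeable errors, N = 4(1.96 + 1.2816)² x (0.1 x 10)/0.5² = 168, or 198 with attrition. A change score gives 212, and first-order autoregressive errors give 850 with attrition. None gives 300. That does not show 300 to be wrong, since alpha and the software settings are not given.

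**Inputs.** 2 x 3 x 4 x 17 = 408 participants, so 34 per site-wave. Visits are at 0, 2, 6, 12 and 18 months. Residual variance is 1 - .9 = 0.1. Let f be the share of variance in estimated person slopes due to site-wave trends common to both arms. Every value of f is an assumption.

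**Baseline standard error.** With time scaled to 18 months, the sum of squares of the visit times is 0.6765. Slope noise per person is 0.1/0.6765 = 0.1478. The standard error of the slope difference is sqrt(4 x 0.1478/408) = 0.0381.

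**Effect of omitting site-wave by time.** With 12 site-waves, the extra slope variance relative to noise is q = [f/(1 - f)] x (408 - 34)/407.
- Person-slope analysis: SE ratio (without the terms over with them) = sqrt(1 + q).
- Random-intercept model as written: the slope is one of four within-person degrees of freedom, so the pooled residual takes up about a quarter of q. SE ratio = sqrt(1 + q/4).

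The true sampling error is unchanged because the shared trends cancel. So for SE ratio r, the test's actual size is 2[1 - Phi(1.96r)]. If the adjusted test has power .90, the unadjusted test has power Phi(3.2415 - 1.96r).

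| f | q | Random intercept: ratio, size, power | Person slope: ratio, size, power |
|---|---|---|---|
| 5% | 0.048 | 1.006, .049, .898 | 1.024, .045, .892 |
| 10% | 0.102 | 1.013, .047, .896 | 1.050, .040, .882 |
| 20% | 0.230 | 1.028, .044, .890 | 1.109, .030, .857 |

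A simulation of this layout (3,000 trials per scenario, no dropout) gave ratios of 1.006, 1.013 and 1.029 for the random-intercept model and 1.024, 1.050 and 1.110 for person slopes. At f = 20% its empirical standard error stayed at 0.0373, against reported values of 0.0391 and 0.0423.

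**The opposite force.** Let g be the share of slope variance belonging to the single class, not shared by the arms (also assumed). With 17 per class, the true standard error grows by sqrt(1 + 16g).
- g = 1%: 1.077, so the reported value is about 1/1.077 = 0.93 of the truth. The simulation gave 0.92, with type I error .071.
- g = 5%: 1.342, so about 0.75. The simulation gave 0.72, with type I error .160.
- Site-wave 5% with class 1%: reported over true 0.92, type I error .073. Adding only the site-wave terms left it at .076.
- Break-even is low: g = 0.1% gives 1.008, already more than the 1.006 from site-wave at 5%.

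**The case against.** **The loss is small.** In the model as written the overstatement is below 3% even at f = 20%. The plan also enrols 400 against a stated need of about 300. Scaling gives 3.2415 x sqrt(400/300) = 3.743, so adjusted power is Phi(3.743 - 1.96) = .963. At f = 10% the unadjusted random-intercept test has Phi(3.743 - 1.96 x 1.013) = .961. This stands.

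**The net direction is not established.** A reader might infer that the reported standard error is too large overall and the test conservative. The documents do not support that. Each arm in each site-wave is a separate class with its own program-trained instructors, and no term represents the class. Instructor differences belong here; they are not balanced by the blocking. Unmodelled variation between persons in slope also makes the random-intercept standard error too small. This stands, and it limits the claim to the omission taken alone.

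**The text is less definite than it looks.** A reader might infer that functional class is the only planned adjustment. That is true of the equation, but it is called the basic model and other covariates are promised elsewhere. Parts of APPROACH, including the opening of the sentence on replications, were not in the text available. This stands as a limit on wording; nothing that can be read adds site or replication.

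**Conclusion.** The point holds as a minor efficiency and specification matter. Site, and by inference replication, structure the assignment, and the basic model carries neither of them nor their interactions with time. Taken alone, the omission overstates the standard error of Plus-by-Time without biasing the estimate. The sizes rest on assumed variance shares, no dropout, linear trends and alpha .05. The larger person-slope figures should not be read as applying to the random-intercept model in the plan; they are the upper end, for an analysis of slopes or change.

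Whether the reported standard error would be too large or too small in total cannot be said from the documents. A class share of 1% would outweigh a site-wave share of 5%.

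**What to change.** State in the Data Analysis section that site and replication (or the 12 site-waves) enter as fixed effects with their interactions with visit, and that functional class enters as a categorical factor. Pair this with a class-level random effect on change, or a cluster-robust standard error by class with a small-sample correction. Without the class term, the smaller residual could make the test anti-conservative.

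Also reconcile the block of about 17 per site in Randomization with the 17 per arm (34 per site-wave) in the sample count, and say whether replication is part of the block, so that the analysis factor is defined.

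Cost: with four follow-up visits, additive site and replication need (2 + 3) + 4 x 5 = 25 extra fixed-effect terms. Full site-wave needs 11 + 4 x 11 = 55. Either is affordable at N = 400. The class term costs more: judged between classes, the arm comparison has 24 - 1 - 1 - 5 = 17 degrees of freedom in the additive form, or 24 - 1 - 1 - 11 = 11 with full site-wave. That favours the additive form. No change to data collection is needed beyond recording site, replication and class for each participant.
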